6.3 Efficacy Assessments

All efficacy assessments will be performed at times defined in the Schedule of Assessments ([Section 3.4](#)).

6.3.1 SLEDAI-2K

The SLEDAI-2K is a validated instrument that measures disease activity in SLE patients at the time of the visit and in the previous 30 days. It is a global index and includes 24 clinical and laboratory variables that are weighted by the type of manifestation, but not by severity. The total score falls between 0 and 105, with higher scores representing increased disease activity. The SLEDAI-2K has been shown to be a valid and reliable disease activity measure in multiple patient groups. A SLEDAI -2K of 6 or more generally represents moderately to severely active disease.⁴⁴

6.3.2 BILAG 2004

The BILAG-2004 index is an organ-specific 97-question assessment based on the principle of the doctor's intent to treat. Only clinical features attributable to SLE disease activity are to be recorded and based on the patient's condition in the last 4 weeks compared with the previous 4 weeks. It will be scored as not present (0), improved (1), the same (2), worse (3), or new (4). Disease activity is graded separately for 9 body systems to 5 different grades (A to E) as follows: A ("Active") is very active disease, B ("Beware") is moderate activity, C ("Contentment") is mild stable disease, D ("Discount") is inactive now but previously active, and E ("Excluded") indicates the organ was never involved.⁴⁴ A shift from BILAG-2004 Grade A or B to a lower grade indicates a clinically relevant change in disease activity as the BILAG-2004 grades mirror the decision points for treatment interventions.

Only investigators that complete BILAG-2004 training will be allowed to perform the BILAG-2004 assessments. Preferably, the same investigator should evaluate the patient at each BILAG-2004 assessment from screening to study completion. The investigator must maintain documentation with descriptive details supporting the BILAG-2004 scoring (eg, chart, worksheet, clinic notes, and labs) at each visit.

See [APPENDIX 5](#) for detailed specifications.

6.3.3 PGA of Disease Activity

The PGA is used to assess investigator's general impression on the patient's overall status of SLE disease activity via visual analogue scale (100 mm) with 0 being "very good, asymptomatic

and no limitation of normal activities” with 100 mm being “most severe possible disease ever seen in all SLE patients”. PGA worsening is defined as an increase of ≥ 30 mm from baseline.

When scoring the PGA, the assessor should always look back at the score from the previous visit.

6.3.4 Composite Endpoints: SRI-4, SRI-5, SRI-6, and BICLA Response

6.3.4.1 SRI-4 Response

The SRI-4 is a composite index of SLE disease improvement that consists of scores derived from the SLEDAI-2K and the BILAG 2004 Index. Response based on the SRI-4 is defined by:

1) ≥ 4 -point reduction in SLEDAI-2K global score, 2) no new severe disease activity (BILAG A organ score) or more than 1 new moderate organ score (BILAG B), and 3) no deterioration from baseline in the PGA by ≥ 30 mm. The SRI-4 response in patients with moderate to severe SLE is associated with broad improvements in clinical and patient-reported outcomes.⁴⁵

6.3.4.2 SRI-5 and SRI-6 Response

Like the SRI-4, the SRI-5 and SRI-6 are composite indices of SLE disease improvement that consists of scores derived from the SLEDAI-2K and the BILAG 2004 Index. However, the SRI-5 and SRI-6 are computed with a minimal five-point or six-point improvement in SLEDAI-2K being required, respectively.⁴⁶

6.3.4.3 BICLA Response

The BICLA is a responder index developed to measure response to therapy, and it includes scores from the BILAG, SLEDAI-2K, and PGA. BICLA response is defined as 1) at least 1 gradation of improvement in baseline BILAG 2004 scores in all body systems with moderate disease activity at entry (eg, all B [moderate disease] scores falling to C [mild], or D [no activity]); 2) no new BILAG A or more than 1 new BILAG B scores; 3) no worsening of total SLEDAI-2K score from baseline; 4) $\leq 10\%$ deterioration in PGA score and 5) no treatment failure.⁴⁴ It is driven primarily by the BILAG, and has been used in Phase 2 and 3 mAb studies.⁴⁷

For the endpoints of BICLA response at Days 210, 240, and 270, patient scores will be completed and response determined.

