4.4 Inclusion Criteria

Patients who meet the following criteria will be considered eligible to participate in this clinical study:

1. Men and women, ages 18 to 70 years, inclusive
2. Patients must be mentally capable of giving consent and there must be evidence of a personally signed and dated informed consent document indicating that the patient has been informed of all pertinent aspects of the study
3. Patients must have SLE as defined by meeting 4 of the Systemic Lupus International Collaborating Clinics (SLICC) classification criteria for SLE (with at least 1 clinical and 1

immunologic criterion or Lupus nephritis as the sole clinical criterion in the presence of ANA or anti-dsDNA antibodies), either sequentially or simultaneously

4. At screening, patients must have at least 1 of the following:
 - a. Elevated ANA \geq 1:80 via immunofluorescent assay at the central laboratory
 - b. Positive anti-dsDNA or anti-Smith (Sm) above the normal level as determined by the central laboratory
 - c. C3 or C4 levels below normal as determined by central lab
5. At screening, the SLE Disease Activity Index 2000 (SLEDAI-2K) must be \geq 6, including points from at least 1 of the following clinical components:
 - a. Arthritis, rash, myositis, mucosal ulcers, pleurisy, pericarditis, and vasculitis
 - i. Excluding parameters which require central laboratory results: hematuria, pyuria, urinary casts, proteinuria, positive anti-dsDNA, decreased complement, thrombocytopenia, and leukopenia
 - ii. Points from lupus headache and organic brain syndrome will also be excluded
6. On Day 0, the SLEDAI-2K must be \geq 6, including points from at least 1 of the following clinical components:
 - a. Arthritis, rash, myositis, mucosal ulcers, pleurisy, pericarditis, and vasculitis
 - i. Excluding parameters which require central laboratory results: hematuria, pyuria, urinary casts, proteinuria, positive anti-dsDNA, decreased complement, thrombocytopenia, and leukopenia
 - ii. Points from lupus headache and organic brain syndrome will also be excluded
7. Patients must have at least 1A or 2Bs from the following manifestations of SLE, as defined by the BILAG criteria as modified for use in this study, which must be confirmed by the central data reviewer:
 - a. BILAG A or B score in the mucocutaneous body system
 - b. BILAG A or B score in the musculoskeletal body system due to active polyarthritis defined as follows:

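### BICLA criterion 1 asks for improvement only in systems with moderate (B) activity, so a patient whose baseline BILAG A never improves can count as a responder

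*Protocol*

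**What the plan says.** Section 6.3.4.3 (current version, V5.0) gives five conditions for BICLA response:

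1. "at least 1 gradation of improvement in baseline BILAG 2004 scores in all body systems with moderate disease activity at entry". The one example is B scores falling to C or D, with B glossed as moderate disease.
2. "no new BILAG A or more than 1 new BILAG B scores".
3. "no worsening of total SLEDAI-2K score from baseline".
4. PGA deterioration of no more than 10%.
5. "no treatment failure".

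Section 6.3.2 fixes the meaning of the grades: A "is very active disease, B ('Beware') is moderate activity". The SRI-4 definition in Section 6.3.4.1 makes the same split, calling A severe and B moderate. Section 6.3.2 also says what counts as meaningful change: "A shift from BILAG-2004 Grade A or B to a lower grade indicates a clinically relevant change in disease activity".

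On entry, Section 4.4, inclusion criterion 7, reads: "Patients must have at least 1A or 2Bs from the following manifestations of SLE". A second B is required only where there is a single B and no A.

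The proportion of patients with a BICLA response is listed among the secondary efficacy endpoints in Section 2.2. Section 8.2.4 compares binary endpoints by Pearson's chi-squared test, and Section 8.2.3 applies the two-sided 0.10 criterion to secondary endpoints as well.

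**The concern.** Criterion 1 is the only one of the five that requires anything to get better; the other four only forbid worsening or failure. Criterion 1 reaches B systems and not A systems. A patient who qualifies on one A and has no B thus has no improvement to show, and in a patient with an A and a B the A is ignored. The rule is stricter on moderate disease than on very active disease, which is at odds with Section 6.3.2, where a fall from A matters just as a fall from B does.

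At stake is the meaning of a tested secondary endpoint. Stable, very active disease can enter the numerator in both arms. That raises both observed rates and, unless stability itself differs enough between arms, shrinks the difference between them.

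**Working it through.** **Definitional check.** The five criteria were applied as written to two body systems, taking SLEDAI-2K and PGA as unchanged and no treatment failure. They were then applied again with baseline A systems brought into criterion 1 and a fall from A to B not treated as a new B.

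| Baseline → visit | As written | A included in criterion 1 |
|---|---|---|
| A/C → A/C | responder | non-responder |
| A/D → A/D | responder | non-responder |
| A/A → A/A | responder | non-responder |
| A/B → A/C | responder | non-responder |
| A/B → A/B | non-responder | non-responder |
| B/B → B/B | non-responder | non-responder |
| B/B → C/C | responder | responder |
| A/C → B/C | responder | responder |

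The first four rows are the defect: the A is unchanged in each. Criterion 2 does not catch them because a persisting baseline A is not new. The fifth row marks the limit: an unchanged B beside the A still blocks response. The last two rows show that genuine improvers are kept.

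**Size.** The protocol gives no BICLA rate, no BICLA power statement and no share of patients entering on an A, so there is no figure of its own to reproduce. Its only power statement is for SRI-4 (Section 8.1). For 132 patients at 2:1 (88 and 44), 65% versus 40%, two-sided 0.10, power comes to 86.6%, in line with the stated more than 80%, and BICLA plays no part in it.

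An illustration needs three assumptions from outside the document:

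- true BICLA rates of 45% (active) and 25% (placebo);
- a share *f* of entrants with an A and no B;
- the proportion *s* of those, in each arm, who meet criteria 2 to 5 and so count under the present wording (called stable below).

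The formulas are:

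- measured rate = (1 − *f*) × true rate + *f* × *s*
- measured difference = (1 − *f*) × 20 points + *f* × (*s* active − *s* placebo)

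Example, *f* = 20% and *s* = 80% in both arms: active 0.8 × 45 + 0.2 × 80 = 52%; placebo 0.8 × 25 + 0.2 × 80 = 36%; difference 16 points.

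Power below is by exact enumeration of the Pearson chi-squared test at two-sided 0.10 with 88 and 44 patients. The undistorted 45% versus 25% gives 74%.

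| *f* | *s* active / placebo | Measured rates | Difference | Power |
|---|---|---|---|---|
| 5% | 80 / 80 | 46.75% v 27.75% | 19 points | 68% |
| 10% | 80 / 80 | 48.5% v 30.5% | 18 points | 63% |
| 10% | 85 / 75 | 49% v 30% | 19 points | 67% |
| 20% | 80 / 80 | 52% v 36% | 16 points | 53% |
| 20% | 85 / 75 | 53% v 35% | 18 points | 62% |
| 20% | 70 / 50 | 50% v 30% | 20 points | 71% |
| 30% | 80 / 80 | 55.5% v 41.5% | 14 points | 45% |
| 30% | 85 / 75 | 57% v 40% | 17 points | 58% |

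The difference shrinks only where stability separates the arms by less than the 20 points assumed for true response. At 70/50 it does not shrink, and power barely moves.

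**The case against.** **The abbreviation eg may leave room for A.** It introduces an example of systems with moderate activity; it does not widen that term, which the protocol reserves for B. It does leave some doubt about intent, but a programmer following the text would code B only.

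**The definition can be settled in the SAP.** Section 6.3.4.3 states the definition outright. What Section 8.2.4 leaves to the SAP is detail such as missing data and medication failures. An SAP that added A would depart from the protocol. Appendix 5 is not in the public text, but it is cited for BILAG scoring, not for BICLA.

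**A persisting A will often be caught by criterion 5.** This has weight. Section 6.3.2 ties BILAG grades to treatment decisions, so an A that persists may well prompt added therapy. Section 4.6.1 bars oral steroid increases above baseline after Day 60 and bars intravenous and intra-articular steroids; Section 4.6.2 bars new immunosuppressants. Section 8.2.3 makes such use a medication failure for the primary analysis. If treatment failure in BICLA means the same, many such patients are already non-responders. That lowers the frequency of misclassification; it does not touch a patient with a stable A who receives no added treatment.

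**A-only entrants may be few.** Also fair. A musculoskeletal A requires assistance with a basic activity of daily living, A and B scores are centrally confirmed, and most active neuropsychiatric disease and severe proliferative nephritis are excluded.

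**Stronger readings.** A reader might infer that an unimproved A makes the patient a responder. It does not: any baseline B must still improve and criteria 2 to 5 must all hold. A reader might also take a fall in power from 74% to 53% as the cost of the wording. That figure needs 20% A-only entrants and no drug effect on stability, and the documents support neither.

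**Conclusion.** Wrong as written, and it should be fixed. The definition can classify a patient with unchanged, very active disease as a BICLA responder while denying that status to an unchanged patient with two Bs. This follows from the protocol's own wording in Sections 6.3.4.3, 6.3.2 and 4.4 and needs no assumption.

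How often it would happen is unknown, because the share of A entrants is not given. The effect on rates and power cannot be computed. Under assumed true rates of 45% versus 25%, the scenarios with 10% to 30% A-only entrants span roughly 45% to 71% power against 74%; dilution of the treatment difference is likely but conditional on how stability differs between arms.

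The reach is one secondary endpoint among many. Neither the SRI-4 primary endpoint nor the sample size rests on it.

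**What to change.** Before unblinding, change two sentences in Section 6.3.4.3:

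- **Criterion 1:** at least one grade of improvement in every body system graded A or B at baseline (A to B, C or D; B to C or D).
- **Criterion 2:** add that a system falling from a baseline A to B is not a new B. Without this, a patient going from A/A to B/B would meet the new criterion 1 but could fail criterion 2 for having more than one new B.

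Criteria 3 to 5 can stand. The cost is a short protocol change and matching lines in the derivation program. BILAG is already collected at Day 0 and at every later efficacy visit (Table 2), so no new data are needed. The downside is that BICLA response rates will look lower in both arms than under the present wording.

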6.3.5 CLASI Response

The CLASI is a comprehensive tool for assessment of disease activity and damage in cutaneous lupus, shown to be valid, reliable, and sensitive to changes in disease activity.⁴⁸ Response is defined as 50% improvement from baseline in “A” or “B” scores. This assessment will be applied to all patients as all are required to have cutaneous disease activity.

For the secondary efficacy endpoint of CLASI response at Day 210, patient scores on MAD and POC studies will be compared with baseline for 50% improvement.

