2.2 Phase 2 Proof of Concept

OBJECTIVES	ENDPOINTS
Primary	

 To demonstrate a superior effect of BOS161721 at the chosen dose compared with placebo for response on the SRI-4 	Primary Efficacy Endpoint 
 The proportion of patients with a SRI-4 response at Day 210 (see Section 6.3.4.1)
Secondary	
To demonstrate a superior effect of BOS161721 at the chosen dose compared with placebo for response on clinical indicators of SLE activity, in adult patients with moderately to severely active SLE on limited background standard of care treatment	Secondary Efficacy Endpoints 
 The proportion of patients with: 
 SRI-4 response at each visit SRI-5 and SRI-6 response at each visit (Section 6.3.4.2) a sustained reduction of oral corticosteroid (CS) (≤ 10 mg/day and \leq Day 0 dose) between Day 120 and Day 210 new BILAG A flare or > 1 BILAG B flares relative to baseline through Day 210 PGA worsening a BICLA response a CLASI response medication failures Results and changes from baseline in: 
 CLASI swollen and tender joints ACR-28 SLEDAI-2K SLICC/ACR damage index Time to medication failure Duration of longest SRI-4 response Time to first SRI-4 response Time to BILAG A flare or > 1 BILAG B flare compared to baseline through Day 210
Safety	

 To assess safety and tolerability of repeat doses of BOS161721 at the chosen dose administered SC in adult patients with moderately to severely active SLE on limited background standard of care treatment 	Safety Endpoints 
 Incidence and severity of adverse events (AEs) and serious adverse events (SAEs), related AEs, AEs leading to study drug discontinuation, AEs by severity and relatedness Injection site reactions C-SSRS 12-lead ECGs parameter results at each visit and change from baseline Vital signs (blood pressure [BP], heart rate, and temperature) parameter results at each visit and change from baseline Clinical laboratory results and change from baseline Physical examinations changes from baseline ADAs Study drug exposure/compliance

Exploratory

• CCI [REDACTED]	
• CCI [REDACTED]

• CCI [REDACTED]	
• CCI [REDACTED]

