3 STUDY PLAN

3.1 Study Design

This is a Phase 1b/2 combined, randomized, multicenter, double-blind, placebo-controlled trial to study the clinical efficacy, safety, and PK of SC doses of BOS161721 in adult patients with moderately to severely active SLE. After successfully completing a screening phase, eligible patients will be randomized to a specified dose of BOS161721 or placebo. The dosing schedule will be monthly.

The trial will consist of 2 double-blinded portions: MAD Phase 1b and POC Phase 2. Patients may receive a total of 7 SC monthly doses of study drug on Days 0, 30, 60, 90, 120, 150, and 180, followed by safety follow-up visits at Days 210, 240, and 270.

SLE disease activity assessment data will be centrally reviewed by medical monitor and sponsor to ensure the scores are clinically meaningful and compliant with specific definition. The scope of responsibility includes, but is not limited to, review and confirmation of “A” and “B” BILAG system organ disease, confirmation of clinical components of the SLEDAI-2K score at screening and during the study, and cross-validation of the instruments used in this study to assess the disease activity. Further details on the content and methods of data reports by the medical monitor and sponsor will be outlined in the Medical Data Review Plan along with the processes and procedures that will be followed.

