6.4 Other Variables

6.4.1 SLICC/ACR Damage Index

The SLICC/ACR damage index is a validated instrument to assess damage, defined as irreversible impairment, continuously persistent for 6 months (ascertained by clinical assessment), occurring since the onset of lupus, and it is based on a weighted scoring system. This index records damage occurring in patients with SLE regardless of cause, with demonstrated content, face, criterion, and discriminant validity.⁴⁹ It will be performed on Days 0 and 180.

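### Section 6.3.5 bases CLASI response on A or B scores that the protocol never defines for the CLASI, so the rule either cannot be computed or does not require improvement in active skin disease

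*Protocol*

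**What the plan says.** Section 6.3.5 introduces the instrument as covering two things: "The CLASI is a comprehensive tool for assessment of disease activity and damage in cutaneous lupus". It then gives the responder rule: "Response is defined as 50% improvement from baseline in “A” or “B” scores". The following paragraph, on the Day 210 endpoint, drops the letters and says that "patient scores on MAD and POC studies will be compared with baseline for 50% improvement", without naming a score. In section 2.2 the endpoint appears among the Phase 2 secondary proportions only as "a CLASI response".

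Elsewhere the letters belong to BILAG. Section 6.3.2 states: "Disease activity is graded separately for 9 body systems to 5 different grades (A to E) as follows". Section 3.1 puts the same two letters in quotation marks when it describes central review: "review and confirmation of “A” and “B” BILAG system organ disease". Inclusion criterion 7 in section 4.4 also uses A and B for BILAG grades.

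The secondary objective in section 2.2 is superiority over placebo on clinical indicators of SLE activity. Section 8.2.4 assigns Pearson's chi-squared test to binary secondary endpoints, and section 8.2.3 applies the primary endpoint's hypothesis, with its two-sided 0.10 threshold, to them.

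**The concern.** A responder rule has to say which score is compared with baseline. Here the score is identified by two letters that have no stated meaning for this instrument, joined by or. Programmers deriving the endpoint from the same data could settle on different meanings and report different response rates. If the letters mean activity and damage, the endpoint can also count patients whose skin disease is no less active.

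At stake is the interpretation of one secondary comparison that carries a formal test. A meaning chosen after unblinding would be open to challenge.

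**Working it through.** The plan gives no figure to reproduce for this endpoint, so the check takes each available meaning of the letters and applies the rule. Percentage improvement is (baseline score − Day 210 score) / baseline score.

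**Reading 1: BILAG grades.** This is the only meaning of A and B that the protocol defines. The grades are ordered letters from A to E. They have no numerical scale, so the formula has nothing to work on and the rule cannot be computed.

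**Reading 2: A is CLASI activity and B is CLASI damage.** The protocol does not state this. It is inferred from the two constructs that section 6.3.5 names. The scores below are assumed, to show the logic only.

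| Activity, baseline → Day 210 | Damage, baseline → Day 210 | Activity improvement | Damage improvement | Rule with or | Activity only |
|---|---|---|---|---|---|
| 10 → 10 | 4 → 2 | 0/10 = 0% | 2/4 = 50% | responder | non-responder |
| 10 → 14 | 2 → 1 | −4/10 = −40% | 1/2 = 50% | responder | non-responder |
| 10 → 5 | 4 → 4 | 5/10 = 50% | 0/4 = 0% | responder | responder |
| 0 → 0 | 4 → 2 | undefined | 2/4 = 50% | responder | undefined |

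The first two rows show response with unchanged or worse activity. The third shows that halved activity does count, so the rule is not blind to activity; it simply does not require activity to improve. The second row also shows that a 1-point change from a baseline of 2 is enough.

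**Reading 3: 50% CLASI improvement among patients who enter with a mucocutaneous BILAG A or B.** Criterion 7a has similar wording. This reading has no separate damage route and no percentage of a letter grade, but it does not say whether activity, damage or some total has to improve.

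**Baseline of zero.** Section 6.3.5 applies the rule to everyone on the ground that skin activity is an entry requirement. Criterion 7 does not impose that: one musculoskeletal A is enough. A patient can therefore enter with a CLASI activity score of 0, for whom the percentage does not exist (fourth row). Any repaired rule has to deal with this case.

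**Other text.** Section 6.3.5 of the V4.0 protocol in the same file carries the same definition, so it does not settle the meaning.

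**The case against.** The strongest reply is that this is loose drafting, not a design fault. Activity and damage are never mapped to A and B, so the damage route rests on inference. Reading 3 is available and avoids both the damage route and the percentage of a letter. Sections 8 and 8.2.4 leave data handling to the SAP, which is not among the documents at hand. CLASI results and changes from baseline are a separate secondary endpoint, so the conclusion on skin disease does not hang on this dichotomy.

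Much of this stands. The mapping is inferred, and the impact is confined to one of many secondary endpoints in a proof-of-concept study. Two parts do not stand. Reading 3 fits the sentence poorly, because the text speaks of improvement in those scores, and it still names no CLASI score. The reference to the SAP does not remove the defect either: sections 6.3.4.1 to 6.3.4.3 set the responder rules for SRI-4, SRI-5, SRI-6 and BICLA in the protocol, and section 6.3.5 does the same for CLASI. The SAP would have to replace a stated rule, not add detail to it.

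**Conclusion.** The point holds as a defective definition. Read with the protocol's own meaning of A and B, the CLASI responder rule cannot be computed. Read as activity or damage, it permits response without improvement in active skin disease. Read as a restriction on who is assessed, it leaves the score unnamed.

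A reader might infer three stronger things, and the documents support none of them:

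- **That a halved damage score must be scoring noise.** Section 6.4.1 does describe damage as "defined as irreversible impairment, continuously persistent for 6 months", but for the SLICC/ACR Damage Index. The protocol says nothing of the kind about CLASI damage.
- **That the rule fails to measure skin activity on any reading.** On the activity or damage reading, a patient whose activity halves is a responder.
- **That the loss can be sized.** If the same fraction f of activity non-responders in each arm qualified through damage alone, each arm's rate would become p + f(1 − p) and the difference would shrink by the factor (1 − f). The protocol gives neither f nor a CLASI response rate, and does not show that f is equal between arms. The 25-point difference in section 8.1 is the planning assumption for SRI-4 and cannot be borrowed.

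The size of any dilution therefore remains unknown and could be close to zero. The conclusion rests on the wording alone.

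**What to change.** Replace the definition in section 6.3.5 with:

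> CLASI response is a reduction of at least 50% from Day 0 in the CLASI activity score, assessed in patients with a Day 0 activity score above 0 (or above a prespecified minimum).

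A minimum above 0 would also limit response decided by a 1-point change from a very low baseline. Report the CLASI damage score separately, as a descriptive change from baseline. Correct the accompanying statement that every patient is required to have skin activity, since criterion 7 does not require it. Make the change before unblinding.

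The cost is a short text amendment. Table 2 already schedules the CLASI at Day 0 and Day 210, so no new data are needed. The downside is a possibly lower response rate and a smaller denominator for this endpoint.

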 - i. “BILAG A:” Severe Arthritis, (BILAG item number 41), manifested by observed active synovitis in \geq 2 joints with marked loss of functional range of movements and significant impairment of basic activities of daily living that has been present on several days cumulatively over the past 30 days, including at the time of the screening visit. See [APPENDIX 5](#) for additional detailed specifications.
 - Basic ADLs are defined as the following activities which require assistance or assistive devices, (at least 1 must be present and documented in source):

- Ambulation, toileting, grooming- including bathing and dressing; feeding oneself
- ii. “BILAG B:” Moderate Arthritis, Tendonitis or Tenosynovitis, (BILAG item number 42), defined as tendonitis/tenosynovitis, or active synovitis in ≥ 1 joint, (observed or throughout history), with some loss of functional range of movements manifested by effects on instrumental ADLs such as:
 - Cooking, driving, using the telephone or computer, shopping, cleaning, etc., and has been present on several days over the last 30 days, and is present at the time of the screening visit

If only one “B” and no “A” score is present in the mucocutaneous body system or in the musculoskeletal body system due to arthritis, then at least 1 “B” must be present in the other body systems for a total of 2 “B” BILAG body system scores

8. Patients must be currently receiving at least 1 of the following:
 - a. Administration for a minimum of 12 weeks, and a stable dose for at least 56 days (8 weeks prior to signing consent) of the following permitted steroid-sparing agents:
 - i. Azathioprine (AZA), mycophenolate mofetil or mycophenolic acid, chloroquine, hydroxychloroquine, or methotrexate (MTX)
 - b. Prednisone (or prednisone-equivalent) cannot exceed 30 mg/day at screening for a patient to be eligible and must be stable at a maximum of 10 mg/day for at least 5 days prior to Day 0 (randomization) (see [APPENDIX 3](#))
9. Women of childbearing potential (WOCBP; see [Section 4.7](#) for full information regarding WOCBP, definition of menopause, and contraception):
 - a. Must have a negative serum pregnancy test at screening. Urine pregnancy test must be negative prior to first dose
 - b. Must not be breastfeeding
 - c. Must agree to follow instructions for method(s) of contraception for the duration of treatment with study drug plus 52 weeks

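### CLASI response is applied to every patient on the ground that all must have skin disease, but the entry criteria impose no such requirement, and 50% improvement is undefined at a baseline of zero

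*Protocol*

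**What the plan says.** Protocol Section 2.2 lists the proportion of patients with a CLASI response among the Phase 2 secondary efficacy endpoints. Section 6.3.5 defines it: "Response is defined as 50% improvement from baseline in" scores labelled A or B. The timing follows: "For the secondary efficacy endpoint of CLASI response at Day 210, patient scores on MAD and POC studies will be compared with baseline". The population is fixed with a reason attached: "This assessment will be applied to all patients as all are required to have cutaneous disease activity".

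The entry criteria are in Section 4.4. Inclusion 7 opens with "Patients must have at least 1A or 2Bs from the following manifestations of SLE" and lists two routes: (a) "BILAG A or B score in the mucocutaneous body system" and (b) "BILAG A or B score in the musculoskeletal body system due to active polyarthritis defined as follows". If only one B and no A is present in skin or joints, a further B "must be present in the other body systems for a total of 2" B grades. Inclusions 5 and 6 require SLEDAI-2K of at least 6 at screening and on Day 0, with points from at least one item of this list: "Arthritis, rash, myositis, mucosal ulcers, pleurisy, pericarditis, and vasculitis".

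Section 8.2.4 tests binary secondary endpoints by Pearson's chi-squared test on the FAS. Section 8.2.3 applies the two-sided 0.10 criterion to them. Section 8.2.1 defines the FAS by treatment received and a post-baseline evaluation, with no reference to baseline CLASI.

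**The concern.** The reason given for including everyone is not true of the population that the protocol admits. Response is defined relative to baseline, so a patient who starts at 0 has no defined outcome and the programmer must choose one. If response is coded as a score no higher than half of baseline, a patient who stays at 0 responds automatically. If a positive reduction is required, response is impossible. In either case these patients carry the same outcome in both arms and pull the difference toward zero.

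A second gap lies in the same sentence. The section describes CLASI as measuring activity and damage, then asks for improvement in A or B scores, which it does not define for CLASI. The score that has to halve is not identified.

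**Working it through.** **1. Does any criterion require skin disease?** Inclusion 7 was enumerated over mucocutaneous grade (A, B, neither), musculoskeletal grade (A, B, neither) and a B in some other system (yes, no), giving 3 × 3 × 2 = 18 combinations. Fourteen qualify. Three of these have no mucocutaneous A or B:

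- musculoskeletal A, nothing elsewhere;
- musculoskeletal A plus a B in another system;
- musculoskeletal B plus a B in another system.

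Inclusions 5 and 6 need points from one listed item. Arthritis is on the list and rash is only one option. Points beyond that item, if needed to reach 6, need not be cutaneous. No inclusion or exclusion criterion sets a minimum CLASI score.

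**2. What happens at zero?** Percentage improvement is (baseline − Day 210) / baseline. With baseline 0 and Day 210 at 0 this is 0/0. Section 6.3.5 gives no rule for the case.

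**3. The plan's own power figure.** Section 8.1 claims more than 80% power for SRI-4 at 65% versus 40% with 132 patients allocated 2:1, that is 88:44, at a two-sided 0.10 level. The test rejects when

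X² = (p̂₁ − p̂₀)² / [p̄(1 − p̄)(1/n₁ + 1/n₀)] > 2.706.

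The normal approximation gives 86.6%, so the claim reproduces. The protocol states no power for CLASI response.

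**4. Illustration for CLASI response.** Let f be the fraction of the FAS with baseline 0. Assume response of 60% (active) and 35% (placebo) in the others. Neither f nor these rates are in the protocol.

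- Counted as non-responders: rates 0.60(1 − f) and 0.35(1 − f) in 88:44.
- Counted as responders: rates 0.60(1 − f) + f and 0.35(1 − f) + f in 88:44.
- Restricted: 60% and 35% in (1 − f) × 88 and (1 − f) × 44 patients.

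Under both codings the difference is 0.25(1 − f). Power is the sum of the binomial probabilities of all outcome pairs for which the test rejects.

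| f | Difference if all counted (points) | Power, counted as non-responders | Power, counted as responders | Restricted n | Power, restricted |
|---|---|---|---|---|---|
| 10% | 22.5 | 79% | 79% | 79:40 | 83% |
| 30% | 17.5 | 64% | 64% | 62:31 | 74% |
| 40% | 15.0 | 56% | 56% | 53:26 | 70% |

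Restriction gives higher power at each fraction although it uses fewer patients.

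**The case against.** The strongest reply is that Sections 8 and 8.2.4 leave data handling for secondary endpoints to the SAP, and that a rule for unevaluable baselines is ordinary SAP content. That holds for the zero-baseline convention, so its absence alone would not be a finding. It does not cover the rest. The protocol is not silent: it names the population and gives a reason that its own criteria contradict. A SAP that restricted the population would depart from that instruction, and no SAP can make the reason true.

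Several stronger readings are tempting, and the protocol does not support them:

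- *Every patient who enters through the joints has a CLASI of 0.* Lack of a mucocutaneous A or B does not show this. Section 6.3.2 describes BILAG grade C as mild stable disease, so milder skin activity may be present. Zero baselines are permitted, and their number is unknown.
- *Joint disease alone suffices for entry.* This holds for the BILAG criterion when the joint grade is A. SLEDAI-2K of at least 6 is also required, and the protocol does not show that arthritis alone reaches it. The remaining points need not come from skin, so the contradiction stands.
- *The A and B scores are BILAG grades used by mistake.* The protocol uses those letters for BILAG elsewhere, but Section 6.3.5 does not say what they mean here. They are undefined, which is all that can be claimed.
- *The trial's conclusion is at risk.* CLASI response enters neither the SRI-4 definition (Section 6.3.4.1), nor the sample size (Section 8.1), nor the superiority decision on SRI-4 (Section 8.2.3).

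**Conclusion.** The point holds as a contradiction between Section 6.3.5 and Section 4.4, together with an incomplete endpoint definition. The contradiction follows from the text alone and needs no assumption. The size of the harm cannot be derived from the protocol. Over an assumed 10% to 40% of patients at zero, with assumed rates of 60% and 35%, the loss from counting them rather than restricting runs from about 4 to 14 percentage points of power (83 − 79; 70 − 56). If few patients start at zero, the loss is small. Because one secondary endpoint is affected and the primary analysis is not, this should be fixed but does not have to be settled before the trial can be interpreted.

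**What to change.** 1. Delete the sentence in Section 6.3.5 that says all patients must have cutaneous activity.
2. State which CLASI score has to fall by at least 50%. The activity score is the natural choice, since the endpoint is meant to show improvement. Remove or define the A and B labels.
3. Analyse CLASI response only in patients whose baseline value of that score is above zero, or at or above a minimum fixed before unblinding. A minimum is the safer option: at a baseline of 1, a one-point fall already counts as 100% improvement.
4. Report the number excluded in each arm.

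Change from baseline in CLASI is a separate secondary endpoint and is defined at a zero baseline, so it can stay in the full FAS. Patients at zero cannot improve there either, which the report should note.

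The cost is wording in the protocol and SAP, and a smaller denominator for this one endpoint. In the illustration above, power rises despite the smaller denominator.
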